4.3 Analysis of Demographic and Baseline Characteristics

Demographic and baseline characteristics will be summarized for the study population overall and by treatment (Abilify MyCite versus virtual matched controls). Discrete variables will be reported as count (frequency) and percent for each category. Continuous level variables (interval, ratio) will be reported as mean and standard deviation. Where applicable, range, minimum, maximum, and median will also be reported.

It is likely that the virtual matched controls will lack some variables that are available to the Abilify MyCite sample. As a result, a comprehensive list of each variable in the Abilify MyCite sample will be listed, while "N/A" will be listed for each variable that is not available in the virtual matched control cohort. Balance in baseline characteristics across the 2 cohorts will be evaluated prior to analysis.

4.4 Primary Endpoint

The primary endpoint is the difference in the proportion of patients with at least 1 all-cause hospitalization for the Abilify MyCite versus virtual matched control cohorts from baseline to Day 180. The primary endpoint analysis will be a McNemar's paired sample chi-square test between the treatment cohorts.

This test is directional in nature as it is testing the alternative hypothesis (H_A) that the proportion patients hospitalized will be lower in the Abilify MyCite cohort than the virtual control cohort. Adjustments will be made to the alpha level to account for the one-tail nature of the alternative hypothesis.

- $H_0: P_1 - P_2 \geq 0$ versus $H_A: P_1 - P_2 < 0$

Where:

- P_1 = proportion of Abilify MyCite patients with all-cause hospitalization from baseline to Day 180
- P_2 = proportion of virtual control patients with all-cause hospitalization from baseline to Day 180

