6.2 Auditing/Inspections

This study may be subject to audits or evaluations by regulatory authorities or Otsuka (or its designee). To enable such evaluations and/or audits, the study physician must agree to maintain and allow reasonable access to required patient and study records. The study physician agrees to keep the identity of all participating patients (sufficient information to link records, eg, hospital records), all original signed ICFs, SAE Forms, source documents, detailed records of treatment disposition, and adequate documentation of relevant correspondence (eg, letters, meeting minutes, telephone calls, reports).

Regulatory requirements for the archival of records for this study necessitate that participating physicians maintain detailed clinical data for a period of 3 years after the end of this study.

7 Statistical Methods and Planned Analyses

Complete details of the planned statistical analysis will be presented in the statistical analysis plan (SAP).

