7.1 Sample Size

The primary endpoint for the study is the proportion of patients with at least 1 all-cause hospitalization from study start date to Day 180. The assumptions for the sample size calculation were based on input from [REDACTED] for patients diagnosed with SCH, BP1, or MDD who had at least 1 all-cause hospitalization or partial psychiatric hospitalization within the 60 days prior to enrollment. A control group event rate of 36.3% was estimated, weighted based on an expected study distribution of 25% patients with SCH, 25% with BP1, and 50% with MDD. Sample size calculations were based on testing 2 proportions using the Z-test with unpooled variance. The study sample size of 447 patients was calculated based on the following assumptions, informed from [REDACTED] 20% reduction in the proportion of patients with all-cause hospitalizations in the Abilify MyCite group versus the virtual matched control group (29.04% Abilify MyCite versus 36.30% virtual matched control), 1:3 (Abilify MyCite : virtual matched controls) matching, 80% power, and maintaining an overall alpha level of 0.05 with the level of significance in a superiority hypothesis of 0.025. Sample size calculations will be documented in the SAP. Using a 30% dropout rate at 6 months, a sample size of 640 patients will need to be enrolled to ensure completion of 447 patients.

A virtual control group of approximately 1350 patients will be identified from the [REDACTED] and matched to the final sample of Abilify MyCite patients. This will create 3 controls for every 1 Abilify MyCite patient, which reduces the required Abilify MyCite sample size as compared to a 1:1 match while maintaining statistical power. Controls will be matched to Abilify MyCite patients using a propensity score derived from [REDACTED]. This process has been shown to minimize bias associated with sample selection. Further details on the matching process will be included in the SAP.

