7.3.1 Primary Endpoint

The primary endpoint compares the proportion of patients with all-cause hospitalizations between the Abilify MyCite and virtual matched control cohorts. The primary endpoint analysis will be a test of independent proportions. Standard methods for these analysis methods were developed by Fleiss and others¹⁵ and included in all statistical software systems.

These tests are directional in nature since the alternative hypothesis is that the proportions in the Abilify MyCite cohort will be lower than the proportions in the virtual controls.

Adjustments will be made to the alpha level to account for the one-tail nature of the alternative hypothesis (H_A).

- $H_0: P_1 - P_2 \geq 0$ versus $H_A: P_1 - P_2 < 0$

Where:

- P_1 = proportion of Abilify MyCite patients with all-cause hospitalization from study start date to Day 180

- P2 = proportion of virtual control patients with all-cause hospitalization from study start date to Day 180

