3.4 Virtual Matched Control Group

Enrolled patients will be matched to a virtual control group in a 1:3 ratio (enrolled patients on Abilify MyCite treatment : virtual matched controls). [REDACTED]

The matching process will be conducted after 6-month study data (or early termination data, if applicable) is collected for all Abilify MyCite patients. The virtual matched control group identified in this process will be used for all study analyses with a small amount of attrition expected for the 12-month analyses for controls who no longer have Anthem insurance coverage.

A pool of potential controls will first be identified using the following criteria:

- ≥ 1 day of enrollment in an Anthem-affiliated commercial, Medicaid, or Medicare health plan with medical and pharmacy benefits during the observation period (from date of First Patient In up until date of Last Patient In)¹³.
- ≥ 1 pharmacy claim for any atypical antipsychotic (excluding Abilify MyCite, clozapine, and long-acting injectable antipsychotics [LAIs]^{14,15}) during the observation period (Appendix F, Tables 2a and 2b).

¹³ Timeframe may be extended if additional samples are needed.

¹⁴ LAIs include: Aripiprazole monohydrate (Abilify Mantenna), Aripiprazole lauroxil (Aristada), Olanzapine pamoate (Zyprexa Relprevv), Paliperidone palmitate (Invega Sustenna), Paliperidone palmitate (Invega Tri state), Risperidone microspheres (Risperdal Consta)

¹⁵ Drugs include: Aripiprazole, Asenapine, Brexpiprazole, Cariprazine, Iloperidone, Paliperidone, Pimavanserin tartrate, Quetiapine fumarate, Risperidone, Ziprasidone, Ziprasidone Mesylate

- ≥ 1 all-cause hospitalization or partial psychiatric hospitalization¹⁶ that occurs at most 60 days prior to a pharmacy claim for any atypical antipsychotic (excluding Abilify MyCite, clozapine, and LAIs).
 - The earliest such pharmacy claim observed after the earliest observed hospitalization will be set as the initial (temporary) index date for each potential control.
 - For patients with ≥ 2 qualifying hospitalization/pharmacy claim episodes, an iterative process will be used to find the best match, and the final index date will be assigned accordingly.
- Age 18 to 63 on index date.
- ≥ 1 claim for SCH, BP1, or MDD on or before index date.
- No claims for pregnancy during the observation period.
- No claims for any LAI during the observation period.
- ≥ 180 days of medical and pharmacy enrollment prior to index date

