4.2 Sample Size Estimation

The primary endpoint for the study is the difference in the proportion of patients with at least 1 all-cause hospitalization for the Abilify MyCite versus virtual matched control cohorts from baseline to Day 180. The sample size calculation assumptions were based on input CCI [REDACTED] for patients diagnosed with SCH, BP1, or MDD who had at least 1 all-cause hospitalization or partial psychiatric hospitalization within the 60 days prior to enrollment. A control group event rate of 36.3% was estimated, weighted based on an expected study distribution of 25% patients with SCH, 25% with BP1, and 50% with MDD. Sample size calculations were based on testing 2 proportions using the Z-test with unpolled variance.

The study sample size of 447 patients was calculated based on the following assumptions, CCI [REDACTED]: 20% reduction in the proportion of patients with all-cause hospitalizations in the Abilify MyCite group versus the virtual matched control group (29.04% Abilify MyCite versus 36.30% virtual matched control), 1:3 (Abilify MyCite:virtual matched controls) matching, 80% power, and maintaining an overall alpha level of 0.05 with the level of significance in a superiority hypothesis of 0.025. Using a 30% dropout rate at 6 months, a sample size of 640 patients will need to be enrolled to ensure completion of 447 patients.

A virtual control group of approximately 1350 patients will be identified CCI [REDACTED] and matched to the final sample of Abilify MyCite patients. This will create 3 controls for every 1

Abilify MyCite patient, which reduces the required Abilify MyCite sample size as compared to a 1:1 match while maintaining statistical power. Controls will be matched to Abilify MyCite patients using a propensity score (please see section 3.4) [REDACTED]. If a sufficient population of controls is not identified to support matching in a 1:3 (Abilify MyCite:virtual matched controls) ratio, the matching ratio will be decreased sequentially to 1:2 followed by 1:1 if necessary.

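### SAP 4.4 names McNemar's test, which is defined for 1:1 pairs, but the plan builds matched sets of one patient and three controls

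*SAP*

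**What the plan says.** **Primary test, SAP 4.4.** "The primary endpoint analysis will be a McNemar's paired sample chi-square test between the treatment cohorts". The hypothesis is one-sided (P1 below P2), with P2 defined as the "proportion of virtual control patients with all-cause hospitalization from baseline to Day 180".

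**Matching, SAP 3.4.** "Enrolled patients will be matched to a virtual control group in a 1:3 ratio". The section adds: "The virtual matched control group identified in this process will be used for all study analyses", with slight attrition allowed for at 12 months.

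**Sample size, SAP 4.2.** About 1350 controls are planned, three per patient. The stated reason for 1:3 is that it creates a design "which reduces the required Abilify MyCite sample size as compared to a 1:1 match while maintaining statistical power". The ratio falls to 1:2 and then 1:1 only if too few controls are found.

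**Protocol.** Section 7.3.1 reads "The primary endpoint analysis will be a test of independent proportions". Section 7.1 reads "Sample size calculations were based on testing 2 proportions using the Z-test with unpooled variance". The opening of Section 7 leaves the full analysis details to the SAP.

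**Status, SAP 5.0 and 5.2.** The study ended after two patients, neither with an efficacy assessment, and the efficacy analysis is marked NA.

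**The concern.** McNemar's statistic is built from discordant pairs: those in which only the treated member had the event, and those in which only the control did. A set with three controls has no single pair outcome. The SAP names no extension to such sets and no rule for choosing one control.

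The two obvious ways of forcing the data into the test both do harm. Counting each patient three times, once against each control, treats dependent pairs as independent and understates the variance. Keeping one control per patient discards two thirds of the control group, although the SAP's reason for 1:3 matching is that the extra controls reduce the number of patients needed.

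The documents also contain three descriptions of the primary comparison that no visible sentence connects: a paired test (SAP 4.4), an unpaired test (Protocol 7.3.1) and an unpaired sample-size formula (Protocol 7.1, SAP 4.2).

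**Working it through.** **Inputs** (Protocol 7.1, SAP 4.2): p1 = 0.2904, p2 = 0.3630, d = 0.0726, 447 completing patients, 1:3 matching, one-sided alpha 0.025 (z = 1.960), 80% power (z = 0.842). The within-set outcome correlation rho is not given, so 0 to 0.3 is assumed throughout.

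**1. The plan's own figure.** p1(1−p1) = 0.2061 and p2(1−p2) = 0.2312.
- The unpooled formula as described gives n = (1.960 + 0.842)² × (0.2061 + 0.2312/3) / 0.0726² = 421.6, so 422.
- Exchanging the two arms' variances gives (1.960 + 0.842)² × (0.2312 + 0.2061/3) / 0.0726² = 446.6, so 447 exactly. The pooled version gives 441.
- At 447 the literal formula has SE = √(0.2061/447 + 0.2312/1341) = 0.02517. Power is Φ(0.0726/0.02517 − 1.960) = 82.2%.
- Dropout: 447/0.7 = 638.6, against a planned 640.

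So 447 is adequate for a comparison of independent proportions at 1:3. None of these variants is a McNemar calculation.

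**2. Each set stacked as m pairs.** Let v be the outcome variance under the null. The numerator per set is mT − ΣC.
- True variance: m²v + mv + m(m−1)rho·v − 2m²rho·v = m(m+1)v(1−rho).
- Variance that McNemar's test assumes: 2mv(1−rho).
- Ratio: (m+1)/2. The factor (1−rho) cancels, so the inflation does not depend on the correlation.
- m = 3: error = 1 − Φ(1.960/√2) = **8.3%**. m = 2: 1 − Φ(1.960/√1.5) = **5.5%**.
- Simulation agrees: 8.3–8.5% and 5.1–5.7%.

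**3. One control per patient (447 pairs).** The probability that both have the event is p11 = p1p2 + rho·√[p1(1−p1)p2(1−p2)]. The discordant proportion is psi = p1 + p2 − 2·p11. Power = Φ[(d√447 − 1.960√psi)/√(psi − d²)].

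| rho | psi | Power |
|---|---|---|
| 0 | 0.443 | 63.7% |
| 0.1 | 0.399 | 68.2% |
| 0.2 | 0.355 | 73.2% |
| 0.3 | 0.312 | 78.7% |

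Power reaches 80% at rho of about 0.32.

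**4. Mantel-Haenszel test stratified by matched set.** With s events among the m+1 members of a set, the expected number for the treated patient is s/(m+1), with variance s(m+1−s)/(m+1)². These are summed over sets. Simulation used 20,000 runs per setting, Gaussian-copula sets and distinct controls in every set. Columns are rho = 0 / 0.1 / 0.2 / 0.3.

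| Test | One-sided error, % | Power, % |
|---|---|---|
| Stratified, 1:3 | 2.6 / 2.6 / 2.6 / 2.5 | 80.7 / 84.6 / 89.0 / 92.6 |
| Stratified, 1:2 | 2.2 / 2.6 / 2.4 / 2.5 | 76.6 / 80.0 / 84.7 / 89.3 |
| Protocol's unpaired test, 1:3 | 2.7 / 2.2 / 1.6 / 1.2 | 81.8 / 82.8 / 84.6 / 86.1 |

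At 1:1 the stratified test and McNemar's test agreed in every run.

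**The case against.** - **The protocol leaves details to the SAP.** It does, and moving from an unpaired to a matched test is a fair refinement. That answers most of the difference from Protocol 7.3.1, where only an explanatory sentence is missing. It does not answer the conflict inside the SAP between Section 4.4 and Sections 3.4 and 4.2.
- **McNemar's test fits the 1:1 fallback.** True, but 1:1 is the last resort, and 447 pairs would then have only the 64–79% power shown above.
- **The SAP never says literally that every control enters the primary test.** Also true. The sentence in SAP 3.4 could be read as saying that one matched cohort serves both the 6-month and 12-month analyses. The sample-size argument in SAP 4.2 nevertheless makes sense only if all three controls are used.
- **Nobody planned to stack pairs or drop controls.** Correct. The figures show what those readings would cost, and the text rules out neither.
- **The protocol's unpaired test would also work.** It keeps the error at or below 2.7% with 82–86% power, so it is defensible. It becomes conservative as within-set correlation rises, and it abandons the matched analysis that the SAP chose.
- **No result was affected.** This stands, and it sets the weight of the point.

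Blacked-out text lies beside the matching description in SAP 3.4 and 4.2, but none is visible in Section 4.4.

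**Conclusion.** The concern holds as a minor one. The primary test named in SAP 4.4 does not fit the planned 1:3 sets. The 8.3% error (5.5% at 1:2) follows from algebra and needs no correlation assumption. The power figures rest on the plan's event rates, 447 complete sets and an assumed correlation of 0 to 0.3. The stratified-test results also assume that no control serves in two sets, which the visible SAP does not state. The sample size is adequate when all controls are used in a suitable test. Because the trial stopped after two patients, the point matters for the written record and for any reuse of this plan.

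**What to change.** In SAP 4.4, replace McNemar's test with a Mantel-Haenszel test stratified by matched set, at one-sided 0.025. It is the direct extension of McNemar's test to several controls per patient, reduces to it at 1:1, and covers the 1:3, 1:2 and 1:1 ratios in SAP 4.2 with one rule. Add a sentence saying that this matched test refines the independent-proportions test of Protocol 7.3.1, and that 447 was derived from the unpaired formula.

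The cost is two sentences and a standard SAS procedure (PROC FREQ with the CMH option, stratified by set). No patients or data are added. Both sentences can sit in the SAP; changing the protocol text as well would need an amendment under Protocol Section 10.

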4.5 Secondary Endpoint

The secondary endpoint compares the difference between groups (Abilify MyCite versus virtual matched controls) in the proportion of patients with at least 80% PDC (with antipsychotic medication) from baseline to Day 180.

4.6 Exploratory Endpoint

NA.

4.1 Missing data

Except where otherwise noted, missing data will not be imputed and will be excluded from the calculation of percentages.

It is likely that the virtual matched controls will lack some variables that are available to the Abilify MyCite sample. As a result, a comprehensive list of each variable in the Abilify MyCite sample will be listed, while "N/A" will be listed for each variable that is not available in the virtual matched control cohort.

4.2 Safety Analysis

All safety summaries will be descriptive in nature.

4.3 Other Analysis

There are no plans to include any other analysis other than what has been described above. Any post-hoc testing that might arise from the results or findings will be discussed and conducted in accordance with standard and accepted statistical procedures.

5.0 STATISTICAL ANALYSES

The study was earlier terminated after two subjects have enrolled and treated in the study; no efficacy assessment was obtained for these two subjects. Thus, only patient baseline information of the two subjects is summarized.

5.1 Study Populations

5.1.1 Enrolled Population

The enrolled population includes all patients who signed informed consent and were enrolled in the study.

5.1.2 Analysis Population

The analysis population includes all patients who met all of the inclusion criteria and none of the exclusion criteria and completed a Day 180 study visit.

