- ≥ 180 days of medical and pharmacy enrollment following index date

Prior to matching, the pool of potential controls and the Abilify MyCite cohort will be stratified by psychiatric diagnosis (SCH, BP1, MDD). The Abilify MyCite cohort psychiatric diagnosis will be based on the psychiatric diagnosis recorded in the eCRF. The potential controls psychiatric diagnosis will be based on the psychiatric diagnosis identified [REDACTED] CCI. In the event that more than one of the qualifying psychiatric diagnoses is identified [REDACTED] CCI, the following hierarchy will be applied to potential controls: SCH>BP1>MDD.

From this pool of patients, combined with the active arm, logistic regression will be used within each psychiatric diagnosis to estimate a propensity score for each patient, where propensity refers to a patient's pre-index likelihood to be in the active arm. The dependent variable equals 1 for patients in the active arm and 0 for the controls. The following variables may be considered for inclusion in the propensity score model; a final determination will be made using descriptive study results on patient baseline characteristics.

- Age
- Gender
- Month of index date
- Plan type (commercial, Medicaid, or Medicare health plan with medical and pharmacy benefits)
- Number of fills for any atypical antipsychotic over 6-12 months prior to index date
- [REDACTED] CCI
- Occurrence/number of visits with a psychiatrist over 6-12 months prior to index date
- Comorbidities over 6-12 months prior to index date

¹⁶ Defined as a medical claim with place of service code = 52 ("Psychiatric Hospitalization"), or with HCPCS codes H0035 or S0201.

- Region of patient residence (Northeast, South, Midwest, West)

The estimated propensity scores will be used to match active arm patients to the virtual controls in a 1:3 ratio. Prior to assessing outcomes, the validity of the propensity score adjustment will be assessed by (1) graphically examining the overlap in propensity scores across treatment and control groups¹⁷, and (2) comparing balance in all baseline characteristics across the cohorts via standardized mean differences. A standardized mean difference >10% in absolute value will be used to indicate potential imbalance that may warrant further investigation or adjustment (e.g. through regression analysis).¹⁸ Propensity score models will be finalized prior to the assessment of outcomes.

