3.5.6 Early Terminations

If a patient withdraws or is withdrawn from the study prematurely (e.g., before completing the scheduled Day 180 or Day 360 visit, if applicable), then an early termination (ET) visit should be performed, at which time all assessments and procedures that were to have been performed at the Day 180 or Day 360 (if applicable) visit should be completed. In such cases, the reason for the ET must be recorded.

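### SAP 5.1.2 defines the analysis population as Day 180 completers; if the primary test uses it, as the sizing implies, the two arms are selected by different post-baseline rules

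*SAP*

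**What the plan says.** **MyCite arm.** SAP 5.1.2, titled Analysis Population, takes patients who satisfied the inclusion criteria and "none of the exclusion criteria and completed a Day 180 study visit". The other two sets are all enrolled patients (5.1.1) and the safety set of patients who started MyCite (5.1.3). SAP 4.4 gives the primary test as McNemar's and names no set. SAP 4.2 sizes the trial on 447 completers out of 640 enrolled, and matches about 1,350 controls to the final MyCite sample.

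**Controls.** SAP 3.4 requires at least "180 days of medical and pharmacy enrollment following index date" and "No claims for any LAI during the observation period", a window defined there as "during the observation period (from date of First Patient In up until date of Last Patient In". There is no visit requirement.

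**Text pointing the other way.** SAP 3.4 also says "Enrolled patients will be matched to a virtual control group in a 1:3 ratio", with matching done "after 6-month study data (or early termination data, if applicable) is collected for all Abilify MyCite patients". For a patient who leaves early, SAP 3.5.6 says "an early termination (ET) visit should be performed", covering the assessments due at Day 180. It does not say whether that visit counts as a completed Day 180 visit.

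**Handling.** The propensity score models a patient's "pre-index likelihood to be in the active arm". The SAP's Missing data section rules out imputation unless stated otherwise, and Other Analysis plans nothing further. Protocol 3.6.3 stops data collection at withdrawal, while footnote h of Protocol Table 3.5.1-1 includes data from baseline to end of study.

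**The concern.** Completing a Day 180 visit happens after baseline, and only MyCite patients can pass or fail it. One ground for withdrawal in Protocol 3.6.3 is intercurrent illness, and the endpoint is hospitalization for any cause, so dropout cannot be presumed unrelated to outcome. If patients who leave are hospitalized more often than those who stay, the completer rate falls without any treatment effect. If they are hospitalized less often, it rises.

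Controls are selected on later events too, but on different ones: keeping insurance, and having no LAI claim in a calendar window that can extend past index. Matching on pre-index variables, with balance checked on baseline characteristics, can neither detect nor remove selection that happens later. At stake is whether the primary difference could be read as a treatment effect at all.

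**Working it through.** **1. The plan's own figures.** Inputs from SAP 4.2: 29.04% vs 36.30%, 1:3 matching, 80% power, level 0.025 (one-sided, given the directional hypothesis in SAP 4.4), 30% dropout.
- Unpooled formula: (0.2904×0.7096 + 0.3630×0.6370/3) × (1.960+0.842)² / 0.0726² = 422. The pooled form gives 441. The stated 447 is close to both and slightly generous (power at 447 vs 1,341 is 82.2% unpooled, 80.6% pooled).
- Dropout: 447/0.70 = 638.6, so 639, against 640 stated.
- Left out by SAP 5.1.2: 640 − 447 = 193, or 30.2%.
- Controls: 3×447 = 1,341 and 3×450 = 1,350, whereas 3×640 = 1,920. The control count is scaled to completers.

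**2. The selection rules side by side (visible text).**

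| | MyCite | Controls |
|---|---|---|
| Follow-up | Day 180 visit completed (SAP 5.1.2) | no visit |
| Coverage | active at entry (Protocol 3.3.4) | 180 days after index |
| LAI | not in use at entry (Protocol 3.3.5) | no claim in the window, before or after index |

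Pregnancy is not counted as a difference: controls with a claim are excluded, and Protocol 3.6.3 makes pregnancy a withdrawal ground.

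How far the LAI filter reaches past index depends on the enrolment window of T days. With index dates evenly spread and T at least 180, the mean share of 180-day follow-up inside the window is 1 − 90/T: 50% for T = 180 and 75% for T = 365 (both lengths assumed).

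**3. Illustration of the error rate.** Assumptions: no true effect, 36.3% true risk in both arms, 30% dropout, dropout risk q, and control filters removing a fraction f of controls who also have risk q. The documents give neither q nor f. The test is the independent unpooled Z-test at one-sided 0.025; SAP 4.4 names McNemar, so the rates are approximate.
- Completer rate c = (0.363 − 0.30q)/0.70
- Filtered control rate b = (0.363 − fq)/(1 − f)
- SE = √[c(1−c)/447 + b(1−b)/1,341]; error = Φ((b − c)/SE − 1.960)

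Example, q = 45% and f = 0: c = (0.363 − 0.135)/0.70 = 0.3257; b − c = 0.0373; SE = 0.02576; Φ(1.447 − 1.960) = 30.4%.

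| q | c | c − b at f=0 (points) | error f=0 | f=10% | f=20% | f=30% |
|---|---|---|---|---|---|---|
| 30% | 39.0% | +2.7 | 0.1% | 0.3% | 0.9% | 2.5% |
| 36.3% | 36.3% | 0 | 2.5% | 2.5% | 2.5% | 2.5% |
| 40% | 34.7% | −1.6 | 8.8% | 6.6% | 4.4% | 2.5% |
| 45% | 32.6% | −3.7 | 30.4% | 18.8% | 8.8% | 2.5% |
| 50% | 30.4% | −5.9 | 63.7% | 40.3% | 16.1% | 2.5% |

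A small gap matters: q = 38.2% against 35.5% in completers doubles the error to 5.0% at f = 0.

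**4. Adding dropouts back without their later data.** Assume no effect, a constant hazard, 30% withdrawing evenly over 180 days, and later events counted as none. The hazard over 180 days is −ln(0.637) = 0.451. The mean event probability before withdrawal is 1 − 0.363/0.451 = 0.195, so 0.195/0.363, or about 54%, of withdrawers' events are seen. The MyCite rate becomes 0.70×36.3% + 0.30×19.5% = 31.26%, and the error at 640 vs 1,920 is 65.5%. Changing the set alone is therefore not enough.

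**5. Power with all initiators and complete outcomes (640 vs 1,920).**
- Effect in everyone: 7.26/2.103 = 3.452; Φ(3.452 − 1.960) = 93.2%.
- No benefit in dropouts: MyCite rate 0.70×29.04% + 0.30×36.3% = 31.22%; 5.08/2.135 = 2.380; power 66.3%.

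**The case against.** **Use of the set is inferred.** SAP 3.4 speaks of enrolled patients and early-termination data. The Day 180 assessments are to be done at the early-termination visit, so that visit might be meant to count. Protocol 3.5.1.7 and SAP 3.5.3 expect every patient to complete Day 180. SAP 5.2 (Efficacy Analysis) reads NA because the trial had ended, which may be why no set was assigned. This stands: a reader might infer that the SAP states a completer primary analysis, and it does not. If completers were never intended, the primary set and the status of early terminations are still undefined.

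**Both arms are conditioned on reaching Day 180.** True in spirit, and the control filters may offset some or all of the bias, as the f = 30% column shows. But a visit and insurance coverage are different conditions, and nothing in the plan makes them select equally.

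**The figures rest on assumed risks.** Also true. A reader might infer that the plan favours MyCite. The documents give no hospitalization risk for dropouts or for filtered-out controls, so no direction is supported. The 36.3% rests on a redacted source; if it already came from continuously covered patients, the f > 0 columns would count that selection twice.

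**Redaction.** Parts of SAP 3.4, Protocol 3.5.1.1, 3.5.1.9, 3.5.4 and 3.6.4, and words in footnote h are not visible. They may bear on coverage, LAI use or data capture after withdrawal. Both the asymmetry and the tension between 3.6.3 and footnote h are therefore judged on visible text only.

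**Conclusion.** The point holds as a gap in the plan. The only set titled for analysis conditions the MyCite arm on a post-baseline visit and would drop about 30% of it. The sizing, the control count and the matching target imply its use for the primary test. Controls are filtered by different later events, the propensity score cannot correct for that, and no sensitivity analysis would reveal it.

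The size is unknown and either sign is possible: about 9% to 64% one-sided error for assumed dropout risks of 40% to 50% without control offset, 2.5% if selection is equal, and about 0.1% if dropouts' risk is 30%. These figures assume no true effect, 30% dropout and an independent Z-test.

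It would be wrong to conclude that a biased result was produced. SAP 5.0 records that the study stopped after two patients with no efficacy assessment, so only the plan is affected.

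**What to change.** - **SAP 4.4 and 5.1.2:** name as the primary set all eligible enrolled patients who initiated MyCite, with their matched controls. Count hospitalizations from baseline to Day 180 whether or not MyCite was stopped or the Day 180 visit took place. State how early-termination patients are counted.
- **SAP 3.4:** apply the same post-index coverage and LAI conditions in both arms or in neither.
- **Sensitivity analyses:** report the Day 180 completer set and the alternative coverage rule.
- **Protocol 3.6.3 and Table 3.5.1-1 footnote h:** reconcile them, checking the redacted text nearby (including 3.6.4), so that hospitalization data to Day 180 are available for withdrawn patients where authorization allows. Otherwise adding these patients back undercounts MyCite events.

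A censoring method, such as Kaplan-Meier 180-day risks with a variance that respects matched sets, is an option if the coverage requirement is dropped. It would need a rule for deaths. It is not a required replacement for McNemar.

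**Cost.** Mostly wording, possibly including consent text (not visible here), and no extra visits. Up to about 1,920 controls instead of about 1,350; SAP 4.2 already allows a lower matching ratio if controls run short. Power must be restated: at 640 vs 1,920 it is 93% if the effect holds in everyone, but 66% if dropouts get no benefit. In the second case 80% power needs (0.3122×0.6878 + 0.3630×0.6370/3) × (1.960+0.842)² / 0.0508², about 887 MyCite patients.
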